## 6.2 Schedule of study procedures: follow-up for subjects who have completed treatment or have discontinued treatment due to toxicity

Evaluation a		
	Month 1	Month 2
Physical examination	X	X
Vital signs (temperature, respiratory rate, blood pressure, pulse)	X	X
Weight	X	X
Urine hCG or serum $\beta$ hCG	X	X
AE/SAE assessment	X	X
Concomitant medications	X	X
ECOG performance status	X	X
Subsequent anti-cancer therapy		X
Hematology	X	X
Serum chemistry	X	X
Thyroid function tests (TSH, and fT3 and fT4) b	X	X

a A follow up visit for evaluation is preferred and will be scheduled monthly for 2 mo after the last administration of pembrolizumab whenever possible.

Alternatively, available data will be collected from medical records and phone evaluation will be attempted as well.

b Free T3 and free T4 will only be measured if TSH is abnormal. They should also be measured if there is clinical suspicion of an adverse event related to the endocrine system.

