The study treatment portion ends for all patients with the last administration of the immunotherapy.

We will monitor and document clinical toxicity per NCI Common Terminology Criteria for Adverse Events version 5.0 during the treatment and for two additional visits 30 days apart from the end of treatment with immunotherapy. Subjects who decline to return to the site for evaluations will be offered follow-up by phone up to 2 months as an alternative and the PI will make every effort to collect toxicity data from medical records.

Patients will be subsequently followed for progression-free survival and overall survival outcomes. Subsequent visits can be accomplished in person or over the phone and clinical and imaging data will be collected from medical records as available.

Patient-reported outcomes will be obtained at each time point using a tailored checklist of PRO-CTCAE head and neck cancer-specific items.

Saliva and blood for correlative studies will be collected before each treatment with immunotherapy for the first 5 administrations and before the quad-shot administration. Saliva and blood samples will only need to be collected on the first day of Quadshot treatment. In the cases in which the patients will receive a 2nd quad-shot and possibly a third quad-shot, blood and saliva will be collected before the respective radiation treatments as well as before the immunotherapy cycles that proceed and follow the quad-shot treatments.

PD-L1 receptors will be tested in all patients as per standard of care. Next generation sequencing is encouraged and will be done whenever possible from the blood or tumor if available.

Quad-Shot Radiotherapy in Combination with Immune Checkpoint Inhibition for  
Advanced/Recurrent Head and Neck Cancer  
Wake Forest Baptist Comprehensive Cancer Center  
WFBCCC60320

If any patient does not complete the study treatment and investigations, the patient will be replaced.

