#### **5.2 Secondary Outcomes**

- 5.2.1 The response rate in the target lesion measured according to RECIST 1.1 (Section 7.1.3).
- 5.2.2 The response rate in the non-target lesions (if applicable) will be measured according to RECIST 1.1 (Section 7.1.3).
- 5.2.3 The duration of response at the target lesion will be defined as the duration from the time measurement criteria are met for CR or PR (whichever is first recorded) until the first date of recurrent or progressive disease as defined in Section 7.1.4.

Quad-Shot Radiotherapy in Combination with Immune Checkpoint Inhibition for  
Advanced/Recurrent Head and Neck Cancer  
Wake Forest Baptist Comprehensive Cancer Center  
WFBCCC60320

- 5.2.4 Progression-free survival (PFS) will be defined as in Section 7.1.5.
- 5.2.5 Overall survival (OS) will be defined as in Section 7.1.5.
- 5.2.6 Tolerability will be measured using the Patient-Reported Outcomes version of the Common Terminology Criteria for Adverse Events (PRO-CTCAE).

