## 6.0 Treatment Plan

### 6.1 Study Calendar

	Screening/ Pre- Registration i	Cycle 1-3 ICI	QuadShot #1	Cycles 4-6 ICI	QuadShot #2	Cycles 7-11 ICI	Quadshot #3	Maintenance ICI Every 3 Weeks
Initial Screening for Eligibility	X							
Informed Consent	X							
Demographics	X							
Medical and Surgical History	X							
Medication List	X							
Comorbidities	X							
Tobacco Use History	X							
Pre-Toxicity Form	X							
Hepatitis A antibody Hepatitis B surface Ag, Hepatitis C antibody and HIV	X							
Urine hCG or serum $\beta$ hCG a	X	As clinically indicated						
Pembrolizumab Administration		X		X		X		X
Quad-shot Radiotherapy h			X		X		X	
Physical Examination b	X	X		X		X		X
Vital Signs	X	X c		X		X		X

Quad-Shot Radiotherapy in Combination with Immune Checkpoint Inhibition for Advanced/Recurrent Head and Neck Cancer  
 Wake Forest Baptist Comprehensive Cancer Center  
 WFBCCC60320

Electrocardiogram d	X	X	As clinically indicated				
Concomitant Medications	X	X		X		X	
Adverse event/serious adverse event assessment				X		X	
ECOG Performance Status	X	X	X m	X	X m		X m
Liver enzyme panel	X	X i		X		X	X
Serum Chemistry	X	X i		X		X	X
Magnesium	X		As clinically indicated				
Uric Acid	X		As clinically indicated				
LDH	X	X i	As clinically indicated				
Amylase, Lipase	X	X i		X		X	X
Thyroid function tests (TSH and fT3 and fT4) e	X	X i		X		X	X
Hematology	X	X i		X		X	X
Urinalysis	X		As clinically indicated				
Coagulation parameters	X		As clinically indicated				
Tumor Assessment with CT scan or MRI f	X		X		X		X
Tumor assessment with PET scan g	X		X		X		X
Blood Collection for Correlatives		X	X	X k	X k	X k	X k
Saliva Collection for Correlatives		X	X	X k	X k	X k	X k
PRO-CTCAE QOL Questionnaire h		X		X		X	X

Quad-Shot Radiotherapy in Combination with Immune Checkpoint Inhibition for Advanced/Recurrent Head and Neck Cancer  
Wake Forest Baptist Comprehensive Cancer Center  
WFBCCC60320

- a. Female subjects of childbearing potential only
- b. Full physical examination at baseline; targeted physical examination at other timepoints

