- h. Prior to cycle 4 (between pembrolizumab cycle 2-3 or 3-4) for all patients. Subsequent quad-shot cycles, if applicable, will be given as follows: quad-shot cycle #2: prior to cycle 8 (between pembrolizumab cycles 6-7 or 7-8); quad-shot cycle #3: prior to cycle 13 (between pembrolizumab cycles 11-12 or 12-13). Radiotherapy shall not be given on the same day as immunotherapy administration. Though specific days are not mandated, it is recommended that at least 1 day of each quad-shot cycle is given within 7 days of the upcoming ICI administration. Only one quad-shot cycle is mandated by the protocol; the 2nd and 3rd cycles may be completed at the discretion of the treating radiation oncologist as per Section 4.3.
- i. Pre-study requirements listed in table must be completed **within** 30 days prior to registration.
- j. If screening laboratory assessments are performed within 3 days prior to Day 1 they do not need to be repeated at Day 1. Results for safety bloods must be available and reviewed before commencing an infusion. Creatinine clearance, gamma glutamyltransferase, magnesium, and uric acid testing are to be performed at screening, on Day 1 (unless screening laboratory assessments are performed within 3 days prior to Day 1), and if clinically indicated.
- k. Blood and Saliva for correlatives will be collected before each of the first five cycles of immunotherapy and before the first quad-shot treatment. Saliva and blood samples will only need to be collected on the first day of Quadshot treatment. For patients treated with subsequent radiotherapy cycles (between ICI cycles 6-7 or 7-8  $\pm$  cycles 11-12 or 12-13) to be collected before the quad-shot treatment and before each ICI cycle administered before and after the quad-shot treatment (ICI cycles 6 and 7 or cycles 7 and 8  $\pm$  before cycles 11 and 12 or 12 and 13)
- l. The PRO-CTCAE
- m. ECOG performance status needs to be collected only on one of the two days of quadshot treatment – either day 1 or day 2.

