### **Severe and Fatal Immune-Mediated Adverse Reactions**

Immune-mediated adverse reactions, which may be severe or fatal, can occur in any organ system or tissue and usually occur during treatment; however, they can also occur after discontinuation. Early identification and management are essential to ensuring safe use of PD-1-blocking antibodies. Monitor for symptoms and signs of immune-mediated adverse reactions. Evaluate clinical chemistries, including liver tests and thyroid function tests, at baseline and periodically during treatment. Institute medical management promptly to include specialty consultation as appropriate.

In general, withhold pembrolizumab for Grade 3 or 4 and certain Grade 2 immune-mediated adverse reactions. Permanently discontinue pembrolizumab for Grade 4 and certain Grade 3 immune-mediated adverse reactions. For Grade 3 or 4 and certain Grade 2 immune-mediated adverse reactions, administer corticosteroids (1 to 2 mg/kg/day prednisone or equivalent) or other appropriate therapy until improvement to Grade 1 or less followed by a corticosteroid taper over 1 month. Consider administration of other systemic immunosuppressants in patients whose immune-mediated adverse reaction is not controlled with corticosteroids. Institute hormone replacement therapy for endocrinopathies as warranted.

**Immune-mediated pneumonitis:** Immune-mediated pneumonitis occurred in about 2.5% of the patients treated with immune checkpoint inhibitors and leads to permanent discontinuation of the drug in about half of the patients. Systemic corticosteroids are required in all patients with pneumonitis. Withhold pembrolizumab for Grade 2, and permanently discontinue for Grade 3 or 4. Resume in patients with complete or partial resolution (Grade 0 to 1) after corticosteroid taper.

**Immune-mediated colitis:** Immune-mediated colitis occur in about 1% of patients receiving immune checkpoint inhibitors leading to permanent discontinuation pembrolizumab in a small percent of patients. Systemic corticosteroids are required in all patients with colitis. Withhold pembrolizumab for Grade 2 or 3, and permanently discontinue for Grade 4. Resume in patients with complete or partial resolution (Grade 0 to 1) after corticosteroid taper.

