### 11.2 Analysis of Secondary Objective

There are 6 secondary outcomes of interest for this pilot study. These are 1) response rate for the target lesion; 2) response rate for non-target lesions 3) duration of response for the target lesion 4) progression free survival (PFS) 5) overall survival (OS) and tolerability assessed using PRO-CTCAE. We now describe our analytic approach for each measure.

For the response rate measures we will estimate the percent of responders (PR or CR) and the corresponding 95% Clopper Pearson exact confidence intervals. For the duration of response, among responders we will estimate both the mean and median duration and the corresponding 95% confidence intervals for the mean and inter-quartile range for the median. For time to event measures (PFS and OS) we will estimate Kaplan Meier survival curves and estimate the median time to event times as well as the percent PFS and OS at 6 months and 1 year post treatment. For tolerability, we will estimate the percent of patients with different AEs assessed using the PRO-CTCAE and corresponding 95% Clopper Pearson exact confidence intervals.

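### PRO-CTCAE is the only analysed tolerability measure, but it is not scheduled after treatment stops, so a patient with no pembrolizumab visit after quad-shot has no planned post-radiotherapy score

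*Combined protocol and SAP*

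**What the plan says.** Objective 2.2.6 is to assess the tolerability of the combination as a way of judging feasibility. Section 5.2.6 names PRO-CTCAE as the measure. Section 11.2 gives the one analysis: "For tolerability, we will estimate the percent of patients with different AEs assessed using the PRO-CTCAE and corresponding 95% Clopper Pearson exact confidence intervals". It states no denominator, time window or rule for missing forms.

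The timing of the form is given in three places:

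- **Section 4.2:** "Patient-reported outcomes will be obtained at each time point using a tailored checklist of PRO-CTCAE head and neck cancer-specific items". The time points are not listed.
- **Section 6.1:** the row "PRO-CTCAE QOL Questionnaire" is marked under the pembrolizumab columns and blank under QuadShot #1. The row carries the marker h, which is the quad-shot timing note. The note that seems meant for it reads only "l. The PRO-CTCAE" and gives no timing.
- **Section 6.2:** this table is for "follow-up for subjects who have completed treatment or have discontinued treatment due to toxicity". It has 11 rows at Months 1 and 2, among them "AE/SAE assessment", performance status, weight and laboratory tests. None is PRO-CTCAE.

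Two further rules bear on who is counted. Section 7.1.1 makes a patient evaluable for toxicity after one radiotherapy fraction and one pembrolizumab cycle. Section 6.6 replaces any patient removed before completing two pembrolizumab cycles, one quad-shot and two further pembrolizumab cycles.

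**The concern.** Section 4.2 places quad-shot in the last week of a pembrolizumab cycle. On the calendar as it reads, the first questionnaire after radiotherapy then falls at the next pembrolizumab visit. A patient who has no such visit moves to the 6.2 schedule, which does not include the form. Whether a post-radiotherapy score exists can therefore depend on whether the patient went on with treatment, and toxicity is one of the reasons for not going on.

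At stake is the secondary outcome meant to inform feasibility. The people most relevant to the question could be missing from the percentages, and the plan does not say how they would be counted. Separately, the protocol follows patients for toxicity for 60 days after the last dose and says of severe immune-mediated reactions: "however, they can also occur after discontinuation". No patient-reported score is scheduled in that period for anyone.

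**Working it through.** **1. Reproduce the plan's own figure.** Section 11.3 gives a maximum exact 95% interval width of 0.52 for 15 patients, at 7/15. The Clopper-Pearson limits for x of n are Beta(0.025; x, n−x+1) and Beta(0.975; x+1, n−x). For 7/15 they are 0.213 and 0.734, a width of 0.521. The figure reproduces. It describes sampling error only and says nothing about forms that were never collected.

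**2. Count the scheduled scores.** Take a patient who receives pembrolizumab cycles 1 and 2 and one quad-shot, and then has no further pembrolizumab visit.

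| Source | Scheduled PRO-CTCAE after quad-shot |
|---|---|
| 6.1, QuadShot #1 column | 0 (blank) |
| 6.1, later pembrolizumab columns | 0 (visits not reached) |
| 6.2, Months 1 and 2 | 0 (no row) |
| 4.2 | undefined |

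This patient is toxicity-evaluable under 7.1.1. The patient has also not had two further pembrolizumab cycles, so if removed from study is replaced under 6.6. The patients affected by the gap are therefore the same ones whose place in the denominator is unstated.

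**3. Illustrate the effect.** Every count here is an assumption. The plan gives none.

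- Five of 15 patients truly have a given severe symptom: 5/15 = 33%. If two of the five have no post-radiotherapy form, the result is (5−2)/(15−2) = 3/13 = 23% among scored patients, or 3/15 = 20% if unscored patients count as having no event.
- Six of 15 truly have it: 6/15 = 40%, exact interval 16% to 68%. With one, two or three of the six unscored:

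| Unscored | Scored patients only | Unscored counted as no event |
|---|---|---|
| 1 | 5/14 = 36% | 5/15 = 33% |
| 2 | 4/13 = 31% | 4/15 = 27% |
| 3 | 3/12 = 25% | 3/15 = 20% |

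- Suppose unscored patients are replaced and only the 15 who continue are reported, at 4/15 = 27%. If each replaced patient had the symptom, the rate over all toxicity-evaluable patients would be 5/16 = 31%, 6/17 = 35% or 7/18 = 39% for one, two or three replaced.

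In the 6/15 example the shift runs from 4 points (40% to 36%) to 20 points (40% to 20%). Every shifted value stays inside the 16% to 68% interval, so the interval would not reveal the problem.

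**4. Check how many patients might be affected.** Section 8.1 reports permanent discontinuation of pembrolizumab for adverse reactions in 5% of patients: 0.05 × 15 = 0.75 patients over the whole of treatment. Table 2 reports grade 3 or higher toxicity with quad-shot of 0% to 14% where given: 0.14 × 15 = 2.1 patients at most. Neither figure is for this combination or for the days after quad-shot. They suggest a small number, possibly none.

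**The case against.** **Toxicity after stopping is recorded.** A reader might infer that the plan is blind to what happens to patients who stop. It is not. Section 4.2 commits to CTCAE v5.0 grading through two monthly post-treatment visits, 6.2 schedules adverse event assessment at both, and 6.5 follows patients removed for unacceptable events until resolution or stabilisation. Severe mucositis would be captured there. This stands. What it does not repair is the analysis, because Section 11 has no table of the clinician-graded data.

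**Section 4.2 may already require the form in follow-up.** Its wording comes after the description of the post-treatment visits and does not exclude them. On that reading 6.2 has dropped a row by oversight. This stands as a possible reading, but staff working from 6.2 would still not collect the form.

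**The calendar is hard to read.** The PRO-CTCAE row, as extracted, is one cell short, so its last mark could belong to QuadShot #3 or to maintenance. The blank under QuadShot #1 is clear, and the point rests on that and on 6.2.

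**The scenario is narrow.** One later pembrolizumab visit gives a post-radiotherapy score. Nothing says the form is given only if the infusion goes ahead, so a patient who attends and is then held could complete it. This stands: the gap is for patients with no such visit at all.

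**The checklist is specific to head and neck symptoms.** Nothing shows that it would detect hepatitis, nephritis or endocrine events. This stands, and laboratory tests and clinician assessment are the tools for those.

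**Conclusion.** The gap and the inconsistency are in the documents. PRO-CTCAE is the sole declared and analysed tolerability measure, 6.2 omits it, 6.1 appears to tie it to pembrolizumab visits, and 4.2 is either contradicted or left unclear. A toxicity-evaluable patient with no pembrolizumab visit after quad-shot has no scheduled post-radiotherapy score, and none is scheduled for any patient in the 60-day follow-up.

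A reader might go further and conclude that reported tolerability will be biased in the treatment's favour. The documents do not establish that. The direction follows only if patients who stop for toxicity have worse symptoms than those who are scored, which is plausible but an inference. The size is unknown, since it depends on how many patients are affected, on the unstated denominator and on how 6.6 is applied. The figures above illustrate sensitivity at n = 15 and are not estimates. In a pilot with no hypothesis test and six secondary outcomes, this is a cheap improvement and not a flaw that undermines the study.

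**What to change.** - Add a PRO-CTCAE row to 6.2 at Months 1 and 2, completed on site or by the phone contact already planned.
- State in 6.1 that the form is obtained at the next scheduled date after each quad-shot, whether or not pembrolizumab is given.
- Complete footnote l, correct the row's marker, and make 4.2, 6.1 and 6.2 list the same time points.
- In 11.2, report PRO-CTCAE over all toxicity-evaluable patients as defined in 7.1.1, including those replaced under 6.6, and give the number without a post-radiotherapy score. Without this, a new row in 6.2 would not settle whether replaced patients count.
- Tabulate the clinician-graded CTCAE data already collected beside the PRO-CTCAE results.

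The cost is two table edits, a footnote and a few sentences in 11.2. The visits or calls already exist, and the form is already held in the study database (Section 13.2). The downside is two to three extra short questionnaires per patient. The change is best made before patients enter follow-up, because the scores cannot be reliably recovered later.

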### **6.3 Treatment Administration**

Systemic therapy (ICI) and radiotherapy will be administered according to the standard of care, according to the treating medical oncologist and radiation oncologist, respectively. Adverse events will be reported according to Section 8 and logged in the AE log.

Medications considered necessary for the patient's well-being may be given at the discretion of the treating physician, i.e., chronic treatments for concomitant medical conditions, as well as agents required for life-threatening medical problems, etc.

### **6.4 Duration of Therapy**

In the absence of treatment delays due to adverse events, treatment may continue one of the following criteria applies:

- Disease progression (not amendable to local therapy),
- Intercurrent illness that prevents further administration of treatment,
- Unacceptable adverse event(s),
- Patient decides to withdraw from the study, or
- General or specific changes in the patient's condition render the patient unacceptable for further treatment in the judgment of the investigator.

### **6.5 Duration of Follow Up**

Patients will be followed for a minimum of 2 times every 30 days after the last study drug is administered for adverse events monitoring. Follow-up for serious adverse events and mortality after the last study dose is administered will take place during the routine clinic visits that the patient will have during the 60-day follow-up window (Also referenced in Appendix D). If no visit occurs during this window, a phone call confirmation should be made to the patient to determine vital status and whether any adverse events and in particular, Grade 4 unexpected adverse events occurred during that window of time and recorded on Appendix F.

Patients will be followed according to the treating physician after removal from study or until death, whichever occurs first. Patients removed from study for unacceptable adverse events will be followed until resolution or stabilization of the adverse event.

Patients will be followed until death for monitoring survival study endpoints. Frequency of visits will be established by the treating physician and will be done in person or over the phone. Tumor imaging will be also performed at the discretion of the treating physician and results will be collected from the medical records. Alternatively, if the patient stops visiting with our clinic, tumor status and survival information will be collected by phone from the patient and from any other oncology office.

### **6.6 Criteria for Removal from Study**

Patients will be removed from study when any of the following criteria apply:

Quad-Shot Radiotherapy in Combination with Immune Checkpoint Inhibition for Advanced/Recurrent Head and Neck Cancer  
Wake Forest Baptist Comprehensive Cancer Center  
WFBCCC60320

- Patient withdrawal of consent or loss to follow-up.
- Adverse event that, in the opinion of the investigator or the sponsor, contraindicates further dosing.
- Subject is determined to have met one or more of the exclusion criteria for study participation at study entry and continuing investigational therapy might constitute a safety risk.
- Pregnancy or intent to become pregnant
- Grade  $\geq 3$  infusion reaction.
- Subject noncompliance that, in the opinion of the investigator or sponsor, warrants withdrawal; eg, refusal to adhere to scheduled visits.
- Initiation of alternative anticancer therapy including another investigational agent.
- Confirmation of PD and investigator determination that the subject is no longer benefiting from protocol treatment.
- Death.

Subjects who are permanently discontinued from further receipt of investigational product, regardless of the reason (withdrawal of consent, due to an AE, other), will be identified as having permanently discontinued treatment.

Subjects who are removed from study prior to completing at least 2 cycles of ICI followed by at least 1 cycle of quad-shot radiotherapy followed by at least 2 cycles of ICI will be discontinued from the study and replaced.

Subjects who are permanently discontinued from receiving investigational product will be followed for safety until follow-up criteria are met in Section 6.4. Subjects who decline to return to the site for evaluations will be offered follow-up by phone for at least 60 days as an alternative.

